## 1. Protocol Synopsis

Full Title	Re-engagement at Discharge 2: Improving post-hospital outcomes for adults with HIV in Zambia (ReCharge 2)
Clinical Trial Phase	N/A
Principal Investigators	[name], MPH [name]
Co- Investigators	[name], PhD [name], PhD, MMed, MSc. [name] [name] [name], MMed [name] [name] [name], MMed [name], MMed [name], RNHNP
Sample Size	N = 100
Study Population	Eligible patients living with HIV hospitalized at University Teaching Hospital or Levy Mwanawasa Hospital, Lusaka, Zambia
Accrual Period	1/1/2023-6/1/2024
Study Design	Single Arm Pre/Post Pilot Study
Study Duration	2 years
Study Agent/ Intervention Description	Community health worker (CHW) follow-up after discharge from hospital
Primary Objective	1. To assess the feasibility and acceptability of CHW follow-up following hospitalization
Secondary Objectives	1. To estimate the potential impact of the pilot program on the proportion who are alive and virally suppressed at 6 months post-discharge 2. To understand implementation factors related to pilot program
Exploratory Objectives	1. To investigate barriers and facilitators to ART adherence for PLHIV following hospitalization 2. To investigate barriers and facilitators to community-based support for PLHIV following hospitalization
Primary Endpoints	1. The proportion of discharged patients who are successfully visited after discharge. 2. The proportion of discharge follow-up visits by a CHW that are comprehensive 3. The proportion of initial post-discharge visits to the ART clinic that are attended by the participant's CHW supporter.
Secondary Endpoints	1. HIV viral load at 6 months post-discharge. 2. Mortality within 6 months of discharge. 3. Retention in HIV care after discharge defined by no gap of >28 days off ART from discharge date to 6 months post-discharge date. 4. ART clinic visit within 1 month of discharge 5. Transition back to ART care at original (pre-admission) clinic

## **2. Background Information and Scientific Rationale**

### **2.1 Background Information**

Hospitalization presents a potential opportunity to alter the long-term outcomes of persons living with HIV (PLHIV) in sub-Saharan Africa (SSA). HIV-related hospital admissions remain common despite mature antiretroviral therapy (ART) programs, and while inpatient mortality rates are 10-30%, an additional 20-40% die within 1 year of discharge. Most hospitalized PLHIV are ART-experienced and had history of poor retention in care and viral suppression. For example, at a central hospital in Zambia, ~90% of hospitalized PLHIV had prior/current ART use (median of 30 months) and 50% of ART-experienced individuals were not virally suppressed, many of whom had disengaged from care. Current inpatient care focuses on stabilization and neglects to understand and intervene on the underlying reasons for suboptimal care engagement that contributed to the hospitalization. Discharge transition of care models for hospitalized PLHIV are virtually non-existent.

### **2.2 Rationale**

Many PLHIV have poor outcomes following hospitalization, including high mortality, readmission, and gaps in HIV care engagement. This is likely multi-factorial and not all etiologies may be modifiable. While high mortality may be due to incurable cancer, the majority of deaths in PLHIV are thought to be caused by infectious diseases for which treatments exist. However, succumbing to these life-threatening infections after discharge may be due to poor understanding of discharge instructions, lack of post hospital care, and poor understanding of required follow up. Psychosocial support also plays a role in the mental and physical health of these sick patients.

In ReCharge 1, we gathered formative data and identified at least three major factors that undermine HIV clinical outcomes after hospital discharge. First, there are gaps in continuity of care between the discharging facility and outpatient. Second, support from family is often suboptimal due to lack of understanding on the cause of illness, lack of HIV status disclosure, and the cost of care. Third, HIV comorbidities may underpin or complicate the immediate reason for discharge or the post-discharge engagement in care. These data were disseminated to local experts in Zambia including from the Ministry of Health and used to create a new care model for post-discharge HIV care. The care model draws from other successful programs in Zambia. In ReCharge 2 we now propose to pilot the program and assess feasibility, acceptability, and potential for clinical impact.

### **3. Literature Review**

It is estimated that 1.2 million people are currently living with HIV in Zambia, representing between 11-12% of the adult population. Urban areas have had a consistently higher percentage of infected people than in rural areas. HIV infection is also higher among females than among males. Of the 1.2 million adults living with HIV, 700,000 (58.3%) were women. The number of AIDS-related deaths since 2010 has reduced by 37%, from 26,000 deaths to 17,000 deaths in 2018, a reduction due to the concerted efforts of the Zambian Government and its global partners in improving access to antiretroviral therapy. Over the past decade, there has been a rapid scale-up of antiretroviral therapy (ART) in Zambia as in other high HIV prevalence settings in Africa. As scale-up programs continue, accessibility to ART has increased tremendously.

Despite the improved access, the number of patients failing therapy with increasing duration of exposure to ART remains high. Factors leading to treatment failure include poor adherence to treatment, prior exposure to antiretroviral treatment with the development of resistance from single dose nevirapine, primary viral resistance, inadequate drug absorption, suboptimal dosing, the complexity of the regimen, inadequate or inconsistent drug supply to mention but a few; the mortality in such patients failing therapy is usually high. Inpatient settings in Zambia continue to have a high burden of HIV, with prevalence of >50% among admitted people.

Hospitalization presents a potential opportunity to alter the long-term outcomes of persons living with HIV (PLHIV) in sub-Saharan Africa (SSA). HIV-related hospital admissions remain common despite mature antiretroviral therapy (ART) programs, and while inpatient mortality rates are 10-30%, most survive to be discharged home. Unfortunately, our team and others in East and Southern Africa have documented that an additional 20-40% of hospitalized people with HIV die within 1 year of discharge. Most hospitalized PLHIV are ART-experienced and had history of poor retention in care and viral suppression. For example, at University Teaching Hospital in Zambia, ~90% of hospitalized PLHIV had prior/current ART use (median of 30 months) and 50% of ART-experienced individuals were not virally suppressed, many of whom had disengaged from care. Current inpatient care focuses on stabilization and neglects to understand and intervene on the underlying reasons for suboptimal care engagement that contributed to the hospitalization. Discharge transition of care models for hospitalized PLHIV are virtually non-existent. Causes of death both during and after hospitalization are not well-understood because of the rarity of post-mortem examinations (especially in out of hospital death); however, most deaths are likely due to common HIV-related opportunistic infections.

Re-engaging patients in HIV care and ART after a period of suboptimal retention has been termed 'using the side door'. 'Side door' patients are underrepresented in HIV program evaluations as their data are censored at initial disengagement. These patients represent a unique population with distinct barriers to reconnect and to re-initiate on treatment, as compared to those using the 'front door' (i.e., proceeding with optimal retention from testing to ART initiation to long-term viral suppression). After hospitalization, long-standing barriers to ART may be exacerbated and new challenges (such as reduced functional status) may arise. These patients need differentiated care models to intensify and optimize their treatment.

## **4. Study objectives**

### **4.1 Primary objective**

1. To assess feasibility and acceptability of a post-discharge CHW follow-up program for adults with HIV

### **4.2 Secondary objectives**

1. To estimate the potential impact of the pilot program on the proportion who are alive and virally suppressed at 6 months post-discharge
2. To understand implementation factors related to pilot program

### **4.3 Exploratory objectives**

1. To explore barriers and facilitators to the HIV care cascade for PLHIV following hospitalization
2. Describe the prevalence of behavioral health comorbidities after hospital discharge among people with HIV
3. To investigate the impact of HIV-associated coinfections and comorbidities on post-hospital outcomes.
4. To explore experiences of community health workers with the delivery of a post-discharge community based CHW follow-up model for adults with HIV
5. To characterize the prevalence of mental health co-morbidities such as depression among PLHIV during and following hospitalization

### **4.4 Primary Endpoints – Program Feasibility**

1. The proportion of discharged patients whose discharge summary is completed
2. The proportion of discharged patients who undergo a home/community visit from a CHW within 1 week of discharge
3. The proportion of discharged patients that attend their recommended hospital follow-up appointment
4. The proportion of discharged patients that carry their discharge summary to their recommended hospital follow-up appointment
5. The proportion of discharged patients who have disclosed their HIV status at least one treatment supporter
6. The proportion of discharged patients who are currently taking the recommended medications for HIV, coinfections, and comorbidities at 1-month post-discharge
7. The proportion of discharged patients who seek relevant services (behavioral health, mental health) following screening and referral

### **4.5 Secondary Endpoints – HIV cascade and clinical outcomes**

1. HIV viral load at 6 months post-discharge.
2. Readmission to hospital within 6 months of discharge
3. Mortality within 6 months of discharge.
4. Retention in HIV care after discharge defined by no gap of >28 days off ART from discharge date to 6 months post-discharge date.
5. Engaged in ART care at a community (non-referral site) clinic at 6 months post-discharge
6. Mental health outcomes (i.e. depression level) post intervention

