#### **5.2.4 Quantitative outcomes:**

Our primary effectiveness outcome will be alive and virally suppressed at 6 months after hospital discharge. Patients who either pass away or have a viral load >60 copies/ml will be considered failures. Patients who are alive but have unknown VL will also be considered failures. Those who transfer care outside of Lusaka District (we expect this to be 2-3%, based on a prior study) will be censored. We will also evaluate numerous secondary outcomes, including retention on ART, defined as possession of ARVs within 30 days of the 6-month post-discharge time point, consistent with PEPFAR TX\_CURR definition. We will also assess ARV adherence (based on medication possession ratio), number of visits attended, and the rate of hospital re-admission.

To ascertain these outcomes, our research assistant will contact the client each month post-discharge to check vital status (alive versus dead) and whereabouts. At 6 months after discharge, we will confirm the location of last HIV care and arrange for patient to have HIV VL, either back at the hospital or at their local clinic. The team will extract electronic medical records from the clinic including visit, pharmacy, and laboratory data, including HIV viral load results. Transfers within Lusaka (where there are 30+ ART clinics) are common and this approach will allow us to have complete end-line data for most clients, including historical controls and pilot participants.

We will also collect implementation outcome data during the trial, such as proportion of trial participants who do not receive any CHW services, the number and type (phone calls, home visits, meetings at the facility) of interactions between participants and CHWs. Semi-structured interviews with a subset of patients will be done to check acceptability of the intervention.

To begin to understand and anticipate meaningful patterns in our pilot data, we will also collect socio-demographics and socio-economic data on patients and their households, as well as capturing extent and severity of co-morbidities. We will include the following measures, captured at the following time points:

At enrollment/in hospital:

- Education (highest completed grade attained) for patient and primary caregiver
- Age, marital status, number of children
- Relationship to household head
- Religion and religiosity (affiliation, frequency of church attendance (weekly))

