## **8. Statistical Considerations**

### **8.1 Sampling frame and Sample Size Calculations**

#### ***8.1.1 Quantitative sample Size***

Our sample size calculation was based on the hypothesis that CHW follow-up will have substantial impact on the proportion who are alive and fully HIV virally suppressed at 6 months. To detect a change in retention from 60% (based on prior studies) to 80% between historical controls and pilot study participants, with a two-sided alpha and 80% power, we would need a sample size of at least 82 pilot participants. We expect that, because of the clinical acuity of participants, some may pass away before discharge occurs, and these would be censored and not included in main analysis. Hence, we will inflate the sample to 100.

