## **8.2 Data Analysis**

### ***8.2.1 Quantitative analysis***

We will describe and compare sociodemographic and clinical characteristics of historical controls and participants. For the primary outcome, we will compare proportions retained in care at 6 months between controls and CHW follow-up recipients, after excluding participants who transferred out. Potential confounders between the intervention and outcome will be adjusted for in multivariable analysis. Sex-stratified models will be fit as secondary analyses, which are important in planning for the follow-on trial. We will compare the proportions who died in each group, as our central hypothesis is that re-engagement in HIV care after hospitalization can lower mortality. We recognize that with a sample size of 100 we will be under-powered for multivariable and sex-stratified analyses (as well as the mortality comparison); however, the point estimates, when interpreted together with feasibility and acceptability data, will be informative and provide support for future use of this intervention.

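### Section 8 sizes and compares on retention, not on the named effectiveness outcome (alive and virally suppressed at 6 months), and retention has two non-interchangeable definitions

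*Combined protocol and SAP*

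**What the plan says.** **The effectiveness outcome.** Section 4.2 sets the effect objective as the proportion alive and virally suppressed at 6 months after discharge. Section 5.2.4 names the same composite as the primary effectiveness outcome and gives its rules: death, a viral load above 60 copies/ml and an unknown viral load all count as failure, and transfers outside Lusaka District (2-3% expected) are censored. The same section lists retention among the secondary outcomes.

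**Section 8.** Section 8.1.1 opens with the alive-and-suppressed hypothesis, then calculates on something else: "To detect a change in retention from 60% (based on prior studies) to 80% between historical controls and pilot study participants". Section 8.2.1 describes its primary comparison as follows: "we will compare proportions retained in care at 6 months between controls and CHW follow-up recipients, after excluding participants who transferred out". It goes on to compare deaths, but it never mentions viral suppression.

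**Retention.** The synopsis and Section 4.5 use a whole-period definition: "no gap of >28 days off ART from discharge date to 6 months post-discharge date". Section 5.2.4 uses a point-in-time definition: "retention on ART, defined as possession of ARVs within 30 days of the 6-month post-discharge time point". Neither part of Section 8 refers to either one.

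**The concern.** An analyst who follows 8.2.1 as written would test a different endpoint from the one in 4.2, 5.2.4 and the first sentence of 8.1.1. The analyst would also have to choose what retained means, with two written definitions to choose from and possibly with the data in view. The 60% from prior studies has the same problem: it could be retention under either definition, or alive-and-suppressed mislabelled as retention.

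This matters even in a pilot. Section 5.2.2 says the comparison with historical controls will inform the sample size of a fully powered trial, and Section 8.2.1 says the point estimates will support future use of the intervention. Both uses need an estimate whose endpoint was fixed beforehand.

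The exclusion rule in 8.2.1 adds a smaller ambiguity. It removes participants who transferred out, without the geographic limit in 5.2.4. That section also says moves between Lusaka clinics are common, and Section 4.5 counts care at a community clinic as an endpoint.

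**Working it through.** **1. Reproduce the plan's figure.** Inputs from 8.1.1: 60% versus 80%, and "with a two-sided alpha and 80% power". The alpha value and the size of the control group are not given; I assume 0.05 and 1:1. The pooled two-proportion formula without continuity correction is

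n per group = [z(0.975) × √(2 p̄ q̄) + z(0.80) × √(p1 q1 + p2 q2)]² / (p2 − p1)²

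With p̄ = 0.70: 2 × 0.70 × 0.30 = 0.42 and p1 q1 + p2 q2 = 0.24 + 0.16 = 0.40. Then [1.96 × 0.648 + 0.842 × 0.632]² / 0.04 ≈ 81.2, which rounds up to **82 per group**. This matches the plan exactly. Power is 0.804 at 82 per group and 0.876 at 100 per group. The inflation to 100 corresponds to 18% loss, since 82 / (1 − 0.18) = 100.

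**2. What if the 60% and 80% do not describe the endpoint analysed?** The documents give no control rate for alive-and-suppressed or for either retention definition. The rates below are therefore assumptions, with the same alpha, power and 1:1 allocation.

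| Control vs pilot | n per group | Power at 82 | Power at 100 |
|---|---|---|---|
| 40% vs 60% | 97 | 0.73 | 0.81 |
| 50% vs 70% | 93 | 0.75 | 0.83 |
| 60% vs 80% | 82 | 0.80 | 0.88 |
| 70% vs 90% | 62 | 0.90 | 0.95 |
| 50% vs 65% | 170 | 0.49 | 0.57 |

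If the 20-point difference holds, the base rate has a modest effect on power. If the difference shrinks to 15 points (last row), the effect is large.

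**3. Compare the two retention definitions on one patient.** A patient has a 40-day gap in month 2, restarts, and holds ARVs at month 6. Under the synopsis and Section 4.5 the patient is not retained, because 40 days exceeds 28. Under Section 5.2.4 the patient is retained.

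The reverse essentially cannot happen among survivors. Someone with no gap over 28 days has held ARVs within 28 days of the 6-month date, and so within 30. The whole-period proportion can therefore only equal or fall below the point-in-time proportion. Neither definition says how a death counts.

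**4. Can the choice of definition move the between-group result?** Illustration with assumed rates and 82 per group, using z = (p2 − p1) / √(2 p̄ q̄ / n):

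- Point-in-time, 60% vs 80%: z = 0.20 / √(0.42 / 82) = 2.79, p = 0.005.
- The no-gap rule moves 10 points of each group to failure, 50% vs 70%: z = 0.20 / √(0.48 / 82) = 2.61, p = 0.009.
- It moves 10 points of controls and 15 of pilot participants, 50% vs 65%: z = 0.15 / √(0.48875 / 82) = 1.94, p = 0.052.

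An equal shift leaves the difference at 20 points and the conclusion unchanged. Only an unequal shift matters, and nothing in the documents says whether one would occur.

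**The case against.** A reader might infer that the study's headline result depends on which retention definition is chosen. The documents do not support that. Sections 4.1, 5 and 5.2.1 make feasibility and acceptability the main goal, and 5.2.4 ranks retention as secondary. Once 8.2.1 uses alive-and-suppressed, the retention definition no longer drives the effectiveness comparison. A different level of retention under the two definitions is also not a different between-group effect, as step 4 shows.

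A reader might also infer that the sample size is wrong. It is not: 82 reproduces exactly under ordinary assumptions.

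The two definitions could be read as two legitimate secondary outcomes, since 4.5 speaks of retention in HIV care and 5.2.4 of retention on ART, and one is essentially a stricter form of the other. That is fair, and both can stay. It does not say which one Section 8 means. The reference to 6 months in 8.2.1 leans towards 5.2.4, but the listed endpoint is the one in 4.5.

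Finally, a reader might infer that 8.2.1 would drop everyone who moved to another Lusaka clinic. Read together with 5.2.4, the exclusion has a narrower meaning, and 5.2.4 describes tracing intended to give complete end-line data for most clients, controls included. What stands is that the two sections use different words for one rule and should agree.

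**Conclusion.** The point holds as an inconsistency in the current text. Section 8 leaves the named effectiveness outcome and substitutes a term with two written definitions, citing neither. The endpoint switch is the main defect; the double definition and the transfer wording follow from it.

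Its numerical effect cannot be calculated from the documents. The illustrations rest on assumed rates, alpha 0.05 and equal groups. They show only that the effect on the between-group difference is nil when both groups shift equally and can matter when they do not.

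This should be fixed before analysis. It does not undermine the pilot's feasibility purpose, and 8.2.1 already accepts low power for its adjusted, sex-stratified and mortality analyses.

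**What to change.** - **8.2.1:** make alive and virally suppressed at 6 months the primary effectiveness comparison, with the failure rules of 5.2.4, and keep it distinct from the primary feasibility endpoints.
- **8.1.1:** state which endpoint and definition the 60% and 80% describe, and give the source of the 60%. State the alpha value and the planned number of controls. If the 60% is not an alive-and-suppressed rate, either justify using it or recalculate.
- **Synopsis, 4.5 and 5.2.4:** keep both retention measures as secondary outcomes under distinct names, for example 'continuous ART, no gap >28 days' and 'on ART at month 6'. State which one 'retained in care' means, including where 5.3.2 stratifies interviews by retention, and state how deaths count in each.
- **8.2.1 exclusion:** replace 'transferred out' with 'transferred outside Lusaka District', to match 5.2.4.

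The cost is wording in the protocol and analysis section. Section 5.2.4 already plans to extract visit, pharmacy and laboratory records and to compute a medication possession ratio, so both retention measures should be derivable without new data collection.

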## 5. Study design

This is a pilot implementation study with a mixed methods evaluation. The primary outcomes are feasibility and acceptability, which will be assessed among participants, CHWs, and other health workers involved in the pilot. Surveys and in-depth interviews (IDIs) will be used as means of collecting data. Secondary HIV care cascade and clinical outcomes, such as mortality, readmission, HIV VL, retention, etc. will also be assessed. Secondary outcomes will be compared, via a single-arm pre/post pilot study, with a comparator group recruited in the recent past (pre-intervention).

